Standard BCHD Linkage Services. The 2007 Maryland HIV/AIDS Reporting Act requires that HIV cases be reported by name. Laboratories are required to report HIV positive tests within 48 hours to the BCHD through PRISM, a morbidity and case management software. Data from PRISM is used to identify new HIV diagnoses and refer cases to a BCDH Disease Intervention Specialist for contact investigations and referral to linkage services. In addition, the Maryland Department of Health (MDH) HIV Surveillance Branch receives laboratory-based reports with results indicating HIV infection (including HIV diagnostic tests, CD4, HIV viral loads, and HIV genotype and phenotype tests) through the enhanced HIV/AIDS Reporting System (eHARS). Using this data, MDH generates weekly “Never in Care” and “Out of Care” lists for BCHD. Guided by these data, the BCDH linkage team contacts patients by phone or in person to connect them to care. Providers can also request assistance from the BCHD LTC program to link patients newly diagnosed or re-engage those lost to HIV care by contacting the LTC team. Therefore, the BCHD linkage officers attempt to contact and provide linkage services to all Baltimore residents newly diagnosed with HIV or who are presumed to be Out of Care or Never in Care, as identified through surveillance data or by referral from providers. Patients who agree to be linked to care by linkage officers are provided a same-day appointment and warm handoff to clinical care (the outreach worker drives the patient to the clinic of his or her choice). After the patient is seen by a provider, the linkage officer can assist with retention to the second appointment, but after the two initial appointments, the LTC officer is no longer involved in the case unless the patient appears again in the MDH Out of Care report at a later time or is referred by a provider. Linkage officers record patient encounters, and linkage attempts and outcomes in PRISM.

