Laboratory Data	HIV surveillance data (Viral load and date) is provided by the BCHD and uploaded to emocha platform	
Laboratory Alerts	Support staff is alerted if participant in the intervention arm has not had a viral load in > 4 months or if the viral load is detectable (> 200 copies/ml)	Support staff contacts participant if alerted
Appointment Alerts	Support staff alerted if no upcoming appointment is documented in the emocha app or the patient responds "No" or does not respond to the question "Did you go to your appointment yesterday" or patient requests help rescheduling appointment	Support staff contacts participant if alerted
Patient initiated messages	Support staff alerted when participant sends message	Support staff contacts participant if alerted

Study Design.

This study is a pragmatic individual randomized trial comparing standard BCHD linkage services or clinic-based linkage and retention and care support services to mLTCR services. The study will not be masked to participants or support staff due to practical considerations, but all data analysis related to Aim 1 will be conducted in a blinded fashion. Figure 2 describes the study design.

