
HIV Surveillance Data Flow. HIV laboratory data (dated viral load) will be used to drive emocha app alerts and for evaluation of primary outcomes. A list of the individuals who have consented to the study (including those recruited in the clinics) will be provided to the BCDH on a weekly basis. The BCHD will send this information to the Maryland Department of Health HIV Surveillance Branch. MDH will generate a weekly report of HIV viral load test results and dates and send this information to the BCDH. The BCDH will share this information with emocha so that it can be uploaded to the emocha platform. Alerts to participants will not include HIV-specific information. HIV surveillance data will be uploaded to the

emocha platform for all participants (intervention and control) and used for data analysis. However, this data will be integrated into the emocha algorithms and alerts only for participants in the intervention arm. Data on all participants will be exported from emocha to JHU secure servers for data analysis.

A backup system will be implemented in the event the MDH or BCHD is unable to generate and/or share the weekly HIV viral load test results. Study team members will access viral load data through health provider records and upload data directly from JHU secure servers to the emocha platform.

Laboratory Assessments. There will be no study-associated laboratory assessments. All laboratory assessments will be conducted as part of clinical care and reported to BCHD HIV surveillance databases (eHARS and PRISM). We will consider those with a suppressed viral load (HIV RNA <200 c/mL) to be fully engaged in HIV care. While some individuals are able to maintain immune control of HIV in the absence of ART, this occurs in <1% of infected persons.

Randomization plan. The study Statistician will generate a randomization schedule to assign 250 participants to each of the study arms with an arbitrary labelling of the arms. All but the data manager will be blinded to the arm assignment to the arbitrary labels initially. When a linkage officer makes the initial contact with an eligible participant /patient, they will introduce the study and if consent to participate is obtained, the officer will telephone the data center to obtain an arm assignment and proceed to enroll the participant. All data analysis will be conducted in a blinded fashion, but the linkage officers and participants cannot be masked from the intervention.

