- b. Secondary outcome variables.
 - 1. Retention in care: Viral load or CD4 count reported in eHARS within a 6 month window of 12 month follow up period (i.e. 3 months before or after 12 month follow up)
 - 2. Mortality: Death occurring within a 6 month window of 12 month follow up period (i.e. 3 months before or after 12 month follow up)
 - 3. Implementation outcomes will include:
 - a. Proportion of out of care or newly diagnosed HIV-infected patients contacted by support staff.
 - b. Frequency of contacts between support staff and patients.
 - c. Qualitative assessments from in-depth interviews with support staff, BCHD/clinic officials, and study participants
 - d. Client satisfaction surveys
- c. Statistical plan including sample size justification and interim data analysis.

Statistical Analysis. For the study's main outcome, we will conduct a test for the equality of proportions of virologically suppressed/not suppressed or missing VL individuals at 12 months between the two study arms, in line with the randomized design of the study. Secondary to this, and to adjust for any residual confounding, we will conduct a logistic regression using individual outcomes (yes/no suppressed) with study arm as a main predictor and adjusting for patient demographic characteristics, socio-economic status at baseline, and other factors. A subgroup analysis will be conducted to assess the effects of the intervention among African-American and people of Hispanic/Latino descent.

Secondary outcomes analysis. An evaluation of the differences in retention in care and participant mortality will follow the same analytical approach as for the main outcome. That is, we will test for the difference in proportions between the 2 arms and a logistic regression will be conducted adjusting for study arm and patient characteristics.

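### Retention counts a viral load or a CD4 count in eHARS, but the described data flow carries viral loads only, so retention cannot be computed as defined from that flow

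*Combined protocol and SAP*

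**What the plan says.** Section 7.b (Secondary outcome variables) counts a participant as retained on a "Viral load or CD4 count reported in eHARS within a 6 month window of 12 month follow up period". The window is 12 months plus or minus 3, so months 9 to 15. Section 7.c gives retention its own comparison of proportions and its own logistic regression.

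The source holds both tests. Under Standard BCHD Linkage Services (section 4.a), the state surveillance branch "receives laboratory-based reports with results indicating HIV infection (including HIV diagnostic tests, CD4, HIV viral loads, and HIV genotype and phenotype tests") through eHARS.

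The transfer to the study is narrower. Under HIV Surveillance Data Flow (section 4.a), "MDH will generate a weekly report of HIV viral load test results and dates". Table 2 describes the upload in the same way: "HIV surveillance data (Viral load and date) is provided by the BCHD and uploaded to emocha platform". The stated purpose is that "HIV laboratory data (dated viral load) will be used to drive emocha app alerts and for evaluation of primary outcomes". The data are loaded for both arms, and "Data on all participants will be exported from emocha to JHU secure servers for data analysis".

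If the weekly report cannot be produced or shared, a backup applies: "Study team members will access viral load data through health provider records and upload data directly from JHU secure servers to the emocha platform". CD4 is not mentioned there either.

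**The concern.** The definition accepts either of two tests, and the route to the analysis file carries one. An analyst who follows the plan would in effect score retention as any viral load in the window. Someone who was in care and had only a CD4 count would be recorded as not retained. If the backup is used, the analyst must also decide, without guidance, whether a viral load found in a provider's record counts as reported in eHARS.

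Retention is named in Aim 1 beside suppression. Both choices would be made after the data are in hand unless they are written down first. Equal loss in the two arms would lower both retention rates and shrink the difference. Unequal loss could shift the comparison in either direction.

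**Working it through.** **1. Definition against data flow**

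| Step | Viral load | CD4 |
|---|---|---|
| Retention definition (7.b) | counts | counts |
| Received by the state through eHARS (4.a) | yes | yes |
| Weekly state report to the study (4.a) | yes | not described |
| Upload to the platform (Table 2) | yes | not described |
| Backup from provider records (4.a) | yes | not described |

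Anyone with a viral load in the weekly report within the window is classified correctly. Two groups are exposed: those with only a CD4 count in the window, and those whose viral load is known only through the backup.

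**2. The plan's own figure**

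The only sample size (section 7.c, Power Calculations) is for suppression: 33% against 46%, 80% power, alpha 5%. With a two-sided test and pooled variance, the mean proportion is 0.395 and

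n per arm = [1.960 × √(2 × 0.395 × 0.605) + 0.842 × √(0.33 × 0.67 + 0.46 × 0.54)]² / 0.13² = 221, or 442 in total.

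This matches the plan and is unaffected by the point. The documents give no retention rate, no retention difference and no CD4-only share, so steps 3 and 4 are illustrations.

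**3. Equal loss in both arms (assumed)**

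Let c be the share of truly retained participants whom the viral-load-only flow misses. Observed retention is p × (1 − c), so the observed difference is the true difference × (1 − c). The 13 points are borrowed from the suppression assumption. Power is for 250 per arm.

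| c | Observed difference (points) | Power, 60% vs 73% | Power, 50% vs 63% |
|---|---|---|---|
| 0% | 13.0 | 0.871 | 0.837 |
| 2% | 12.7 | 0.851 | 0.819 |
| 5% | 12.4 (13 × 0.95 = 12.35) | 0.819 | 0.793 |
| 10% | 11.7 (13 × 0.90) | 0.762 | 0.746 |

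If true retention is the same in both arms, equal loss leaves the difference at zero.

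**4. Unequal loss (assumed)**

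With equal true retention p, the spurious difference is p × (control loss − intervention loss). Taking p from 50% to 70%, control loss of 5% to 10% and intervention loss of 2% to 5%, the scenarios run from 0.50 × (0.05 − 0.02) = 1.5 points to 0.70 × (0.10 − 0.02) = 5.6 points in favour of the intervention.

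The one feature of the plan that could produce this pattern is the alert in Table 2. Staff are prompted when an intervention participant has no viral load for more than 4 months, and controls trigger no such prompt. That could make CD4-only participants rarer in the intervention arm. No figure in the documents shows that it does.

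**The case against.** The strongest reply is that this is silence, not contradiction. The described feed is said to serve alerts and primary outcomes, and retention is not named. Nothing makes the platform the only analysis source: mortality, another secondary outcome, comes from the National Death Index. The state already holds CD4 results, so a separate extract for retention may simply have gone unmentioned. This stands in part. A reader might infer that retention cannot be computed at all, and the documents do not support that. But the export sentence covers the analysis data without exception, and no section brings CD4 to the study.

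Three other inferences go too far:

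- **Backup results fail the eHARS condition.** Laboratory Assessments (section 4.a) says "All laboratory assessments will be conducted as part of clinical care and reported to BCHD HIV surveillance databases (eHARS and PRISM"). A viral load found in a provider's record may therefore also be in eHARS. What is missing is a rule for checking and counting it.
- **The backup would be searched more thoroughly for intervention participants.** Surveillance data are loaded for both arms, and the backup replaces a report built from the list of everyone who consented. Only the alerts are limited to one arm. Equal searching is not stated, but unequal searching is not suggested either.
- **The primary outcome has the same fault.** It needs only a viral load, and section 7.a sets no eHARS condition. A viral load missed under the backup would count against suppression, but nothing in the plan shows that this would happen or would differ by arm.

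It is also fair to say that the backup is a contingency, and that the illustrated losses have no source in the documents.

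**Conclusion.** The narrower point holds. From the data flow described, retention cannot be computed as section 7.b defines it. It reduces to any viral load in the window, and the standing of backup results is left open.

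The size cannot be determined from the documents. It is negligible if few participants have a CD4 count without a viral load in months 9 to 15. Under an equal 5% to 10% loss, an assumed 13-point difference would read 12.4 to 11.7 points. Those figures rest on assumed loss shares and on a difference taken from the suppression endpoint. Bias between arms is a possibility arising from the intervention-only alert, not a finding. The CD4 gap concerns a secondary outcome and leaves the primary outcome and its sample size untouched.

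**What to change.** - Ask the state health department to add CD4 results and dates to the eHARS extract for all randomized participants in both arms, covering months 9 to 15, and compute retention from that extract.
- If the backup is used, state that provider-record results count by the same rule, and search for every participant in both arms.
- Add a sensitivity analysis of retention on eHARS results alone, where these are available.

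Defining retention by viral load alone would also remove the contradiction. However, it changes the outcome, and it ties retention to the one test that the intervention alert prompts, so adding CD4 is preferable.

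The cost is one more field in a data request to a source that already holds it, a few sentences in sections 4.a and 7.b, and a little more analysis work.

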According to modelling studies, improvement in linkage and retention in care indicators is the single most important component to achieve the 2020 National HIV/AIDS Strategy targets and substantially reduce the burden of HIV in the United States.ⁱⁱⁱ The results of this randomized study will contribute to the evidence on the effectiveness of mHealth-enhanced LTCR initiatives implemented by the local health department and clinics. Evidence supporting the feasibility and effectiveness of this intervention will be important for HIV clinics, the BCHD and other health departments as they allocate limited resources to address the HIV epidemic in their jurisdictions. The information will also be relevant to Ryan White officials responsible for allocating federal dollars to support clinical and ancillary services to improve HIV outcomes, particularly among patients who are uninsured or underinsured.

2. Objectives

Aim 1: To compare virologic suppression and retention in care between HIV-infected individuals who are randomized to receive standard of care linkage and care support services versus mHealth-enhanced LTCR (mLTCR) services. The primary outcome measure will be virologic suppression

at 12 months of study enrollment, and secondary outcomes will include retention in care at 12 months.

Aim 2: To examine the implementation of mLTCR services using a mixed-methods approach to determine the intervention's feasibility, acceptability, coverage, fidelity, sustainability, and patient satisfaction.

3. Background

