Clinic-based Linkage and Retention Services. In response to the “End the HIV Epidemic” strategy, many HIV clinics have strengthened their HIV Linkage and Retention Services. The Johns Hopkins Bartlett Clinic, for example, has implemented a Rapid ART initiation (RART) protocol where patients who are newly diagnosed with HIV in the Emergency Department and linked to the clinic within 1 business day with same-day ART initiation at the time of visit. In addition, the clinic uses “Data-to-Care” to identify patients who are out of care (no visits for > 8 months) or whose viral load is not suppressed, and provides them patient navigation services, appointment reminders, and pharmacy/adherence support.

mHealth-enhanced LTCR (mLTCR). This approach leverages the existing BCHD and clinic-based LTC and support protocols to identify newly diagnosed patients, those out of care, and those in need of retention services to provide ongoing linkage and retention to care services for 12 months. The intervention has an mHealth LTCR application based on an existing evidence-based HIPAA-compliant mHealth application facilitates direct communication and linkage between support staff such as outreach workers or patient navigators and patients, allowing for two-way communication to improve coordination of care and timely treatment. The app allows support staff and patients to communicate over time. In contrast to standard BCHD Linkage services, where linkage officers provide two-time support to link patients to care, the mLTCR approach will promote ongoing engagement between support staff and a patient over a period of 12 months. This allows for repeated doses of support (patient and algorithm-driven) and provides more opportunities for patients to develop a trusting relationship with support staff. The communication between patients and support staff will be driven by the patient’s needs. Patients will be assigned a specific support staff member to allow for relationship-building, with backup as needed for support staff absences,

vacations, and sick leave. The BCHD linkage officers and clinic-based patient navigators are representative of the community served (primarily African American or bilingual Latino) and have long-standing experience working with the community.

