Mortality Assessment. Participants will be cross referenced with the Center for Disease Control and Prevention's National Death Index, a database for all deaths in the United States, to determine if there is a known date of death and cause of death.

Implementation Assessment

RE-AIM Framework. Using a hybrid study design, we will also incorporate implementation science evaluations to assess important implementation questions while also assessing effectiveness. Hybrid designs are efficient approaches to obtaining information that can help understand research findings in terms of internal validity and external generalizability, and provide data to facilitate translating research into real world policy and programs. We propose using the well-established RE-AIM Framework for implementation science research to provide methodological specificity for Aim 2. This framework was created to encourage consideration of program elements that can improve the sustainable adoption and implementation of effective, generalizable, and evidence-based interventions.

A summary of how the 5 components will be assessed in this proposal is shown below.

Summary of mHealth-enhanced LTCR implementation evaluation using the RE-AIM approach

Component	Research Question	Assessment Method(s)	Outcome(s) of Interest
Reach	Who received the intervention?	Program Data	Proportion of out of care or newly diagnosed HIV-infected patients contacted by linkage officers.
Effectiveness	What impact did the intervention have on outcomes?	End-of-study viral load	See Aim 1.
Adoption	Did the community and providers adopt the intervention?	Program data, In-depth interviews	Frequency of contacts between support staff and patients. Services provided/received.
Implementation	Was the intervention delivered as intended?	Program data, In-depth interviews	Roll-out program fidelity.
Maintenance	Was the intervention sustained over time?	Program data, In-depth interviews	Consistent implementation and effectiveness over time. Retention.

Support staff and patient navigators in-depth interviews. In an effort to measure the intervention's feasibility and degree of fidelity, we will conduct in-depth interviews (IDIs) with support staff (N=5) before and 12 months after the implementation of the mLTCR intervention to allow for sufficient time for staff to acclimatize to service delivery and to give ample time to adapt services based on feedback.

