The control group will receive usual linkage and retention to care services provided by the BCHD or the participant's clinic. The objective of the trial is to determine the benefit of delivering mHealth enhanced, longitudinal linkage to care and retention services.

f. Definition of treatment failure or participant removal criteria.

Not applicable

g. Description of what happens to participants receiving therapy when study ends or if a participant's participation in the study ends prematurely.

Participants randomized to the intervention arm will receive mHealth-enhanced LTCR services for a year. Following the 12 month follow up, patients will receive usual BCHD LTC services or clinic-based retention and care services. The BCHD or clinics may decide to continue to provide mHealth-enhanced LTCR services beyond the patient's 12 month enrollment in the study based on the studies interim analysis of effectiveness, patient satisfaction and cost.

5. Inclusion/Exclusion Criteria

Enrollment criteria for RTC:

Eligibility criteria include:

1. ≥ 18 years of age
2. Ability to provide consent
3. Identified by BCHD Linkage protocol to be a new HIV diagnosis or HIV-infected and "out of care" or referred by HIV clinic-based patient navigator, nurse, or provider.

Exclusion criteria include:

1. Excluded due to insufficient facility using a smartphone based upon participant and/or study staff assessment during enrollment process.

Enrollment criteria for in-depth interviews

Participant meets one of the following criteria:

1. Participant in the RTC, OR
2. Linkage to care officer, OR
3. Patient navigator, OR
4. Other support staff members, e.g. nurses
5. Stakeholders at the Baltimore City Health Department (BCHD) who has administrative or programmatic input on HIV services

6. Drugs/ Substances/ Devices

a. The rationale for choosing the drug and dose or for choosing the device to be used.

Not applicable

- b. Justification and safety information if FDA approved drugs will be administered for non-FDA approved indications or if doses or routes of administration or participant populations are changed.
Not applicable
- c. Justification and safety information if non-FDA approved drugs without an IND will be administered.
Not applicable

7. Study Statistics

- a. Primary outcome variable. Virologic suppression: Viral load < 200 copies/cc within a 6-month window of 12 month follow up period (i.e. 3 months before or after 12 month follow-up).

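### The secondary mortality outcome counts only deaths in months 9 to 15, so deaths in the first nine months are never mortality events and mortality over the 12-month follow-up is not measured

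*Combined protocol and SAP*

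**What the plan says.** Section 7b item 2 of the combined protocol and SAP defines mortality as "Death occurring within a 6 month window of 12 month follow up period (i.e. 3 months before or after 12 month follow up"). The parenthesis fixes the interval at months 9 to 15 after enrolment.

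The same window appears in two other outcomes:

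- **Primary outcome (section 7a):** "Viral load < 200 copies/cc within a 6-month window of 12 month follow up period".
- **Retention in care (section 7b item 1):** "Viral load or CD4 count reported in eHARS within a 6 month window of 12 month follow up period".

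On analysis, section 7c states: "An evaluation of the differences in retention in care and participant mortality will follow the same analytical approach as for the main outcome". That means a test of two proportions and an adjusted logistic regression. No denominator is given for mortality, and there is no rule for participants who die before month 9.

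The Mortality Assessment paragraph in section 4a links participants to the National Death Index "to determine if there is a known date of death and cause of death". It does not limit the deaths sought to any window. The description of the intervention in section 4a says that it is "to provide ongoing linkage and retention to care services for 12 months".

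Mortality is not the primary outcome. Aim 1 in section 2 says "The primary outcome measure will be virologic suppression".

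**The concern.** A window of three months either side of month 12 suits a laboratory value. Viral load can be measured repeatedly, and the window says which measurement represents month 12. Death is a cumulative event, and its natural measure is the proportion dead by a given time since randomisation. A window that opens at month 9 leaves out the first nine months of the intervention and takes in three months after it ends.

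The unstated denominator leaves two readings:

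- **All randomised participants.** This is the fairer inference, because mortality follows the approach for the main outcome. A participant who dies in month 4 is then a non-event, grouped with the survivors.
- **Participants alive at month 9.** The comparison is then conditional on survival to month 9, which is itself a post-randomisation outcome.

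Under either reading, a difference between arms that arises in months 0 to 9, whether benefit or harm, is not registered as a difference in deaths. The outcomes also disagree with each other. A participant who dies in month 4 has no viral load in the window and so falls in the not-suppressed-or-missing group of the primary analysis, but is not a death in the mortality analysis.

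**Working it through.** **The plan's own figure.** The documents size nothing on mortality. The only design figure is 221 per arm (442 in total), from suppression of 33% v 46%, 80% power and 5% alpha (section 7c, Power Calculations). Taking the test as two-sided with pooled variance and no continuity correction:

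n = [1.960 × √(2 × 0.395 × 0.605) + 0.842 × √(0.33 × 0.67 + 0.46 × 0.54)]² / 0.13² = 220.8, rounded up to 221 per arm.

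This reproduces the plan and does not depend on the mortality definition.

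**Inputs for mortality.**

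- From the documents: window of months 9 to 15 (section 7b item 2); intervention of 12 months (section 4a); 250 per arm, 500 in total (section 4a, Randomization plan; section 7c).
- Assumed, because the documents give no death rate: 12-month mortality r of 1%, 2%, 3% or 5%, and the shape k of the hazard over time.

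**Formulas.** With t in years, S(t) = exp(−(ht)^k), and h is set so that 1 − S(1) = r.

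- Risk in the window = S(0.75) − S(1.25)
- Share of deaths to month 15 left out = 1 − [S(0.75) − S(1.25)] / [1 − S(1.25)]
- Share of deaths to month 12 left out = [1 − S(0.75)] / [1 − S(1)]

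**Worked case: r = 3%, constant hazard (k = 1).** h = −ln(0.97) = 0.03046. S(0.75) = 0.97741, S(1) = 0.97000, S(1.25) = 0.96264.

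- Window risk, all randomised: 0.97741 − 0.96264 = 0.01477, or 1.48%
- Window risk, survivors to month 9: 0.01477 / 0.97741 = 1.51%
- Mortality to month 12: 3.00%; to month 15: 3.74%
- Share of deaths to month 15 left out: 1 − 0.01477 / 0.03736 = 60%
- Share of deaths to month 12 left out: 0.02259 / 0.03000 = 75%

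**Expected deaths in 500 participants, constant hazard.**

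| Assumed 12-month mortality | Counted by the rule (months 9–15) | Deaths to month 12 | Deaths to month 15 |
|---|---|---|---|
| 1% | 2.5 | 5 | 6.2 |
| 2% | 5.0 | 10 | 12.5 |
| 3% | 7.4 | 15 | 18.7 |
| 5% | 12.2 | 25 | 31.1 |

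About half of the counted deaths fall in months 12 to 15, after the intervention has ended.

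**Sensitivity to the hazard shape (r from 1% to 5%).** Share of deaths to month 15 left out:

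- Falling hazard, k = 0.5: about 78%
- Falling hazard, k = 0.7: about 70%
- Constant hazard, k = 1: about 60%
- Rising hazard, k = 1.3: about 52%

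**Two illustrations of the comparison between arms (250 per arm, 3% control mortality, constant control hazard).**

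| Assumed effect | Deaths to month 12, control v intervention | Deaths counted by the rule |
|---|---|---|
| Hazard halved in months 0–9 only | 7.5 v 4.7 | 3.69 v 3.74 |
| Hazard halved throughout | 7.5 v 3.8 | 3.7 v 1.9 |

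In the first case the difference disappears. In the second the risk ratio is almost unchanged (0.504 to month 12, 0.508 in the window), but about half of the events are lost and approximate power falls from 20% to 12%.

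**The case against.** The strongest points on the other side concern weight.

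1. **The relative comparison is biased only if the effect varies over time.** With a halving of the hazard throughout, the window keeps the risk ratio at about 0.51. This stands. The protocol does not say when a mortality effect would arise, so neither illustration can be preferred. In the constant-effect case the window still costs precision and gives the wrong absolute level.
2. **The correction would rarely change a test result.** With an effect confined to months 0 to 9 and 3% control mortality, a cumulative 12-month outcome has about 12% power at 250 per arm. This stands. It does not justify discarding events when they are already few.
3. **Early deaths are not lost to the trial.** They count as failures in the primary analysis through the missing viral load. This stands for suppression, but there they cannot be told apart from other missing values, and it does nothing for the mortality outcome.
4. **Mortality has low standing here.** Aim 1 names only retention among the secondary outcomes, and no early stopping rule depends on mortality. This stands, and limits the severity.
5. **The understatement depends on the comparator.** Against month 15 the count is always too low if any deaths occur before month 9. Against month 12, the deaths added in months 12 to 15 partly offset those omitted. The count is about 49% of the 12-month total at 3% under a constant hazard, 64% at k = 1.3 and 98% at k = 2. This also stands. Even where the totals nearly agree, the deaths counted are largely different deaths.

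The sponsor may have meant any death up to month 15. The parenthesis says otherwise, no other section gives a cumulative definition, and that intent would need the same correction.

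**Conclusion.** The concern holds. Followed exactly, the plan never counts a death in months 0 to 9 as a mortality event, and under neither possible denominator does the result measure mortality over the 12-month follow-up. Under an assumed constant hazard about 60% of deaths to month 15 are left out, with a range of about 52% to 78% for Weibull shapes 1.3 to 0.5. All counts rest on assumed death rates, because the documents give none.

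The certain consequences are that early deaths go uncounted and that the figure reported as mortality does not describe a period starting at randomisation. Distortion of the relative effect is conditional on an effect that changes over time. This is a secondary outcome for which the trial was not sized, so the estimate will probably be imprecise under any definition. The point should be fixed, but it does not threaten the primary conclusion.

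**What to change.** Rewrite section 7b item 2 so that mortality is death from any cause from randomisation to a fixed horizon, and state that the denominator is all randomised participants. Month 12 matches the intervention period, with deaths to month 15 as a supporting figure. The choice between these horizons matters less than starting the clock at randomisation.

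In the Mortality Assessment paragraph of section 4a, state that the National Death Index search covers the whole period from randomisation to that horizon, since no search period is given now.

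The planned comparison of proportions can stay. An exact test is sensible if deaths are few, and the adjusted logistic regression should then be read with caution. A time-to-event analysis is optional.

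The cost is one line of definition, the denominator and the search period. Dates of death are already planned, so no new data source, visit or participant is needed, and the sample size does not change.
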